## 4.3. Purpose of the study

With this study we propose the performance of a prospective registry of pulmonary vein cryoablation in subjects with paroxysmal or persistent AF at Spanish sites.

# 5. Study objectives and endpoints

## 5.1. Objectives

#### **5.1.1.** Primary Objective

To evaluate the efficacy of the cryoablation procedure at 12 months, defined as the absence of recurrences of atrial fibrillation.

#### 5.1.2. Secondary Objectives

- Description of the profile of subjects who undergo this type of procedure (demographic factors, cardiovascular risk factors, medication, physical activity, sleep apnea, alcohol, smoking, chronic pulmonary disease, obesity, etc.).
- To evaluate the acute efficacy of the procedure: complete isolation of the pulmonary veins demonstrated by the successful electrical disconnection of the pulmonary veins in the cryoablation procedure.
- Description of the complications related to the procedure.
- To evaluate the use of healthcare resources which this cryoablation procedure entails.

#### **5.1.3.** Ancillary Objectives

It is considered that the participating sites may send proposals for additional analyses during the course of the study as long as they do not interfere with the primary or secondary objectives.

## 5.2. Endpoints

## **5.2.1.** Primary endpoint

The primary and secondary endpoints coincide with the primary and secondary objectives defined in section 6.1.

## 6. Study Design

It is an observational, prospective, national study of subjects who undergo pulmonary vein cryoablation. All subjects (as long as they meet the I/E criteria) who undergo pulmonary vein cryoablation for atrial fibrillation will be enrolled at Spanish sites with demonstrable experience of the technique (at least 10 procedures a year), anonymously and with a secure web form.

#### 6.1. Duration

It will last approximately 3 years: 2 years of enrollment and 1 year of follow-up. The follow-up period may be increased if it is deemed necessary for the progress of the study by the Scientific Committee and the Sponsor.

# 7. Product Description

Arctic Front Advance® cryoballoon connected to a nitrous oxide conveying system and inserted through a steerable sheath (FlexCath Advance®) from Medtronic. The device is CE marked and will be used according to the IFU for the pulmonary vein cryoablation. In accordance with standard clinical practice, any devices available on the market at that time with the CE mark and having the indication of pulmonary vein cryoablation may also be used.

The devices will not be provided as part of the study by the Sponsor. Sites will use those commercially available at their sites.

# 8. Subject selection

# 8.1. Study population

The sample size will be approximately 1000 subjects who must be enrolled over the two-year period, based on the annual rate of cryoballoon ablations carried out in Spain.

All local and regional regulatory requirements must be met before the activation of each site and before the enrollment of subjects in the study. Each participating site should have the official confirmation from the sponsor authorizing them to start any study activity. Enrollment will last for 2 years. It is expected to commence in May 2016 and finish in May 2018.

A subject will be considered to be enrolled in the observational study from the moment in which he/she signs the Data Release Form for the study.

The investigator will keep a register of all the subjects enrolled in the study, linking each subject to a specific identification code for that site and that subject. This code will be assigned automatically by the electronic Case Report Form and will not contain any of the subject's personal information, so that the anonymity of the participating subjects is assured.

## 8.2. Subject enrollment

Those subjects who meet ALL of the inclusion criteria and none of the exclusion criteria may be enrolled in the observational study.

Subjects will be considered as included in the study from the moment they sign the Data Release form providing consent to collect their data.

Patient files for those subject enrolled in the registry will need to be clearly identified as subject participating in clinical study.

#### 8.3. Inclusion criteria

- Signature of the Data Release Form
- Subjects ≥ 18 years old
- Subjects who meet the indication for the Cryoballoon Ablation procedure.

#### 8.4. Exclusion criteria

- Subjects with a life expectancy of less than 12 months.
- Subjects who meet the exclusion criteria defined by local legislation (e.g., age, pregnancy, breastfeeding, etc.).
- Subjects who may currently be enrolled, or who plan to take part, in a study with a drug
  or device that may cause bias during the course of this study. Co-participation in
  concurrent trials is only allowed when documented pre-approval is obtained from the
  Medtronic study manager.

# 9. Study Procedures

It is an observational study whereby the participating sites will carry out the cryoablation procedure in accordance with standard practice at their site. During this baseline procedure and during follow-up, there are no related additional tests and only the data deemed necessary according to the Case Report Form will be collected.

#### 9.1. Schedule of events and data collection

Clinical data will be collected at specific times throughout the observational study. The data will be collected through an electronic data collection system for clinical trials (eCRF).

The collection of data can only be carried out once the subject has signed the Data Release Form for the study. The requirements for the collection of data are shown in Table 1.

The variables collected from the subjects will be as follows:

Version 1.0 11/APR/2016 **RECABA** 

#### **Baseline procedure:**

- 1.- Demographic factors, cardiovascular risk factors (arterial hypertension, diabetes mellitus, dyslipidemia, smoking), physical activity, sleep apnea, body mass index.
- 2.- Evolution time of the arrhythmia, previous anti-arrhythmic treatments, previous cardioversions.
- 3.- Anatomical data arising from the imaging tests (left ventricular parameters, ejection fraction, ventricular wall thickness, diameter, area or volume of the left atrium, pulmonary vein drainage pattern, pulmonary vein diameters)
- 4.- Procedure variables: number of applications per vein, application time, registration of pulmonary vein potentials during the ablation, time to block the vein, minimum temperature reached, reheating time, isolation or not of the pulmonary vein, results of the adenosine test, procedure time, exposure time to radioscopy, complications, temperature details in each of the applications, temperature at the time of isolation.

#### Annual follow-up (+/- 28 days):

5.- Variables during follow-up: anti-arrhythmic treatment, clinical recurrence of arrhythmia, result of the continuous ECG monitoring, 12-lead ECG, Nuubo monitoring method, etc. according to the protocol for each site.

A blanking period of 3 months has been established.

**TABLE 1: Data collection requirements** 

	Inclusion	Baseline visit	Procedure	Follow-up
IC signed and dated	x			
Subject demographics		X		
Medical history		X		
Cardiovascular medication		X		X
Echocardiography		X		
Pulmonary anatomy		X		
Procedure data			X	
AF monitoring test				x
Healthcare resource utilization			X	x
Adverse Events	When it occurs			
Study Exit	When it occurs			

## 9.2. Investigation Site Selection

An investigation site may be included in the observational study if the site meets the following requirements:

- > The site has demonstrable experience of the technique (at least 10 procedures a year),
- > The site has adequate resources, facilities, equipment and support staff
- > The site is capable of complying with the requirements of the registry, laws and local regulations, as well as Medtronic's requirements

According to local requirements a Clinical Trial Agreement or Investigator agreement will be in place depending on site specifics.

In order to document investigator experience and qualification a current (within 2 years) CV from the investigators will be collected

## 9.3. Subject Informed Consent – data release form

The investigator or designee must inform the subject about everything related to the observational study, using words which can be understood by the subject.

The investigator must give the Data Release Form to the subject and it must be signed and dated, in duplicate, by the subject him/herself (or by a legal representative) and by the investigator of the observational study, before carrying out any type of activity related to the registry or before making use of the subject's personal information.

The subject must keep a copy duly signed and dated by both parties. The Investigator will keep the other copy in the archives for the observational study at the site, duly signed and dated.

The subject must be given the opportunity to check the details of the observational study and to have adequate time to decide whether he/she wants to take part in the observational study or not. The investigator must respond to all the questions that the subject may want to ask.

The details of the observational study can only be sent to the sponsor after the signature process of the Data Release Form.

Personal data will be processed at all times with due confidentiality and privacy, and in accordance with the applicable regulations on data protection and privacy, in particular in compliance with Spanish Organic Law 15/1999, of December 13, 1999, on personal data protection and with its secondary legislation, including Royal Decree 1720/2007, of December 21, 2007, Regulation implementing Organic Law 15/1999 and Law 41/2002, of November 12, 2002, on basic regulations for subject autonomy.

In accordance with current legislation, the subject may exercise his/her right to access, correct, delete and object to his/her personal data to the Principal Investigator, who will direct his/her request to the person responsible for the archiving of personal data at the hospital or to the sponsor. The request must specifically include the following: name, last name(s), copy of the requester's identification document, the study in which he/she is participating, description of his/her request and an address recorded for carrying out the process.

# 9.4. Training requirements

Prior to the activation of the investigation site in the study, Medtronic will provide relevant and pertinent training about the study for the personnel involved in the conduct of study activities and the investigator's responsibilities.

Training will be provided on:

- Clinical Investigation Plan (CIP)

Version 1.0 11/APR/2016 **RECABA** 

- Signature process of the Data Release Form.
- Database management
- Applicable local regulations

## 9.5. Study materials and study specific equipment

The following material will be provided to each site for the performance of the study:

- Investigator's File
- Access to the electronic Case Report Form (CRF)
- Hard copy of subject worksheets with study-specific data to be collected.

The sponsor will not provide any medical devices used in this registry since it is an observational study.

There is no study specific equipment as the equipment used per standard of care is the one to be used.

#### 9.6. Safety assessment

The products used have the CE mark and are used under the authorized indications for use according to their label. However, it is the investigator's responsibility to comply with any requirements for the reporting of Adverse Events (AE) as required by the Clinical Investigation Plan, by local legislation, and the specific requirements of each EC.

The investigators of this registry will report any deficiencies/malfunction and any adverse events related to the medical device through the regular channel from the vigilance system. As part of Medtronic's continual post-marketing safety assessment, Medtronic will evaluate those experiences and events and will produce monitoring reports for the local competent authorities as required.

In this registry, the adverse events will be reported through the eCRF. The investigator must enter all the information on the eCRF as soon as possible and before 10 calendar days from awareness date of the event, as long as the regulatory authorities do not require stricter timelines.

#### 9.7. Data collection

The investigator and the members of his/her team must ensure the accuracy, integrity and authenticity of the data entered on the CRF. The sites will have the option to collect study data using the site worksheets, although the use of these is optional.

The data will be collected through an electronic data collection system for clinical trials. To facilitate the task of data collection, the sites will have paper copies of the sites' worksheets that contain the required information in accordance with the Clinical Investigation Plan for optional use in case the data are not captured elsewhere in the patient file. These will be stored in the study files.

The data entered on the CRF will come from the source documents and will be consistent with them. The investigation site team will create and store the source documents (such as the subject's clinical records, the ECGs, the subject's medical records, laboratory results, etc.). Only the persons authorized by the principal investigator may complete the CRF and only the investigator or designee authorized by the Principal Investigator may sign the CRF..

The Electronic Data Capture system maintains an audit trail on entries, changes or corrections in CRFs. If an individual authorized to complete the CRF makes changes to a CRF that has already been signed, the investigator must go sign the CRF again.

#### 9.8. Protocol deviation handling

Because it is an observational study where the site's standard clinical practice is to going to be studied, and the protocol is drafted on that basis, no deviations from the protocol are foreseen.

Investigator must not deviate from the CIP.

In case there is any specific PD related to CIP or Good Clinical Practice (such as subject not signing Data Release Form and subject data collected) a PD form will be completed in the CRF and corrective/preventive actions will be identified.

Protocol Deviations will need to be reported to local ECs per local requirements.

## 9.9. Subject withdrawal or discontinuation

The study investigators can decide to remove the subject from the study in the following situations:

- Loss to follow-up over the course of the study. A patient will be considered as lost to follow after 3 attempts have been done to contact the patient without success and those are appropriately documented in the source documents
- Does not meet inclusion/exclusion criteria.
- The investigator thinks that it would be advisable for the subject to leave the study.

On the other hand, the subject has the right to terminate his/her participation in the study at any time during the course of the study.

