#### 10. Risks and benefits

#### 10.1. Potential risks

Because it is an observational study of marketed products, there are no additional risks through participating in the study.

In the study, the products will be used in accordance with their labeling, therefore no risks different from those normally associated with standard clinical practice of the device are foreseen.

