## 13.1. Analysis of clinical data

It is expected to include approximately 1000 subjects enrolled at approximately 30 Spanish sites, with an enrollment period of 2 years and a follow-up period of one year from the time of enrollment of each subject. The subjects analyzed will be the ones included in the RECABA study database: "Spanish Registry of Cryoballoon Ablation". The variables analyzed will be those mentioned previously with the intention of adequately describing the activity of the clinical sites, the procedures used and the diseases treated in accordance with standard clinical practice.

All the data are anonymized in origin so that it is not possible to identify the subjects.

The collection of data will be prospective from the time of enrollment.

The database will be received codified and debugged, and the allocation of the lost values that have been decided previously.

The basic report at the end of enrollment and at the end of the follow-up period will consist of: The quantitative variables are expressed as mean, median, typical deviation and interquartile range depending on which is most suitable for the distribution of values. The differences between groups in relation to the quantitative variables will be evaluated through the student t test for independent samples or the analysis of variance (depending on the number of groups compared) and between variables through the student t test for related samples or the analysis of variance of repeated measures, as applicable. To analyze the relationships between categorical variables the chi-squared test ( $\chi^2$ ) and the Fisher's exact test will be used. The differences of proportions will be assessed through the homogeneity test  $\chi^2$ . To assess the relationships between the quantitative variables the Pearson or Spearman r correlation will be used, as appropriate.

The intermediate statistical reports proposed by the investigators will depend on the hypotheses suggested by the investigator. They will include at least a descriptive analysis such as the one described previously. In addition, the appropriate models to respond to the hypotheses proposed will be estimated, which can include techniques of the style of exploratory factor analysis, analysis of multiple contingency, analysis of logistical regression, analysis of conglomerates or analysis of multifactorial variance.

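### Protocol 9.9 lets investigators remove already ablated subjects, and neither document says whether removed subjects stay in the 12-month denominator; removal related to prognosis would raise the AF-free percentage

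*Protocol*

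**What the plan says.** Protocol 9.9 opens with "The study investigators can decide to remove the subject from the study in the following situations" and lists three. Loss to follow-up has an objective test: three documented contact attempts. The other two are "Does not meet inclusion/exclusion criteria" and "The investigator thinks that it would be advisable for the subject to leave the study". These carry no time point, trigger, documentation rule or sign-off. The subject's own right to stop is stated separately: "the subject has the right to terminate his/her participation in the study at any time during the course of the study".

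Protocol 8.2 sets the start: "Subjects will be considered as included in the study from the moment they sign the Data Release form". Section 9.9 therefore applies from before the procedure to the end of follow-up. The exclusions in 8.4 include "Subjects with a life expectancy of less than 12 months", pregnancy, and planned participation in another drug or device study.

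On analysis, Protocol 13.1 says "The subjects analyzed will be the ones included in the RECABA study database". The SAP (Statistical models) calculates the number and percentage without recurrence after 12 months, taking recurrence from the Follow-up and Adverse Events tables. It defines no denominator. The SAP (Treatment of missing values) assumes non-response is MCAR and, for status over time, carries the last valid status forward. The Study exit table holds only a reason and a date.

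**The concern.** The primary result is one percentage with no comparator, so a selective loss of subjects cannot cancel between arms. Some grounds for removal can be linked to how the subject is doing. A severe complication could shorten life expectancy, a return of AF could lead to a plan to join another study, and an opinion that leaving is advisable can rest on anything. If such subjects leave and their later recurrence is never recorded, the AF-free percentage rises. AF-related events after 30 days and follow-up resource use would be lost in the same way.

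The discretionary ground has no evident protective purpose in this registry. Protocol 9 adds no tests, Protocol 10.1 states that "there are no additional risks through participating in the study", and a subject who wishes to leave already can. Removal by the investigator changes no treatment; it ends data collection.

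**Working it through.** **No figure in the plan to reproduce.** The documents give no removal rate, expected success rate or precision target. The sample of about 1000 (Protocol 8.1) rests on procedure volume. All rates below are assumptions.

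**Where information can be lost**
- Protocol 11.2 collects recurrence after the blanking period on the adverse event form, with eCRF entry before 10 calendar days from awareness. The SAP reads that table, so a recurrence known and entered before exit can count.
- A recurrence after removal, or known but not yet entered, is not captured.
- Table 1 places the AF monitoring test at follow-up. A subject removed earlier does not contribute that visit, so a recurrence that only the test would show is also missed.

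**What the SAP then does.** Let N be the number ablated, p the true AF-free proportion, and k the number of subjects with recurrence who are removed with it unrecorded.
- Dropped under MCAR: Np/(N − k) if no AF-free subject is removed.
- Carried forward as recurrence-free: (Np + k)/N.
- Kept with the recurrence recorded: p, so no bias.

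**Illustration 1: N = 1000, p = 75%, 2% of AF-free subjects also removed**
- AF-free subjects remaining: 750 × 0.98 = 735.
- 8% of recurrences removed: 250 × 0.92 = 230. Dropped: 735/(735 + 230) = 735/965 = 76.2%, a shift of +1.2 points.
- 15% removed: 250 × 0.85 = 212.5. Dropped: 735/(735 + 212.5) = 735/947.5 = 77.6%, a shift of +2.6 points.
- Same removals carried forward: (750 + 20)/1000 = 77.0%, and (750 + 37.5)/1000 = 78.75%.
- 95% half-width: 1.96 × √(0.75 × 0.25/1000) = 2.7 points.

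**Illustration 2: N = 1000, only subjects with recurrence removed**

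| True AF-free | 95% half-width (points) | k = 50, dropped | k = 50, carried forward | k at which bias equals half-width (dropped / carried forward) |
|---|---|---|---|---|
| 60% | 3.0 | 63.2% | 65.0% | 48 / 30 |
| 70% | 2.8 | 73.7% | 75.0% | 39 / 28 |
| 80% | 2.5 | 84.2% | 85.0% | 30 / 25 |

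With k = 10 at 70%, the result is 70.7% (dropped) or 71.0% (carried forward). A handful of removals hardly matters; a few dozen matter as much as sampling error. Each removed subject whose recurrence was already entered, and is counted, reduces the shift.

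**The case against.** A reader might infer that subjects can leave once their outcome is known and that this outcome is then irrecoverable. The documents do not support that. A recurrence the investigator knows about is due on the eCRF before 10 calendar days from awareness, and the SAP uses that table. Nothing says a removed subject's data are deleted, and leaving the study is not the same as leaving the analysis. For a recurrence after the blanking period to be both known and unrecorded, it must fall within the entry window or the site must have missed the deadline. Procedure-related events are collected only up to 30 days, so a removal in month 6 does not lose them. This objection stands, and it limits the point to events after removal or not yet entered.

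A reader might also take Protocol 9.9 to give investigators an express power to remove at any time. Those words describe only the subject's own right. For investigators, the section simply sets no limit.

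The ordinary reading of the eligibility ground is that the subject was ineligible at enrolment, since Protocol 8.2 uses the criteria to decide who may be enrolled. That is probably what was meant. But 9.9 does not say so, and this reading does nothing to confine the discretionary ground.

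Finally, the removal rates are assumed. The higher one implies about 52 removals (15 + 37.5), with recurrences removed at 7.5 times the AF-free rate (15%/2%). That is fair, and no rate is claimed as likely.

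**Conclusion.** The point holds in a limited form. Two removal grounds are open after ablation, and no rule says whether removed subjects are followed, retained or counted. The resulting bias is possible, not certain. It requires that removal be related to prognosis or early outcome, and that the recurrence occur after removal or be unentered at exit. Under those conditions, dropping the subject and carrying the subject forward both raise the AF-free percentage.

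The size cannot be known from the documents. Under the assumed rates in Illustration 1, 75% becomes 76.2% to 77.6% if removed subjects are dropped, or 77.0% to 78.75% if they are carried forward. The half-width is 2.7 points. The exit reason and date allow removals to be counted afterwards, but they do not supply the missing 12-month outcome. The change is worth making because it protects the primary result at almost no cost.

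**What to change.** **Protocol 9.9, eligibility ground.** Limit it to subjects found not to have met the criteria as they stood when the Data Release Form was signed. State that conditions arising after the procedure are not grounds for removal.

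**Protocol 9.9, discretionary ground.** Either delete it, or require a documented reason that is not based on rhythm outcome or complications. Either choice is defensible.

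**Protocol 9.9 and SAP, Statistical models.** State that:
- every ablated subject with valid consent stays in routine-care follow-up and in the primary denominator, including one found ineligible in error, who is recorded as a deviation under Protocol 9.8;
- all data up to any exit are retained, subject to the deletion right in Protocol 9.3;
- exits are reported by reason and by recurrence status at exit;
- removed subjects are censored at exit in the Kaplan-Meier analysis and not carried forward as recurrence-free.

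Censoring alone is not a cure, because it assumes that exit is unrelated to later recurrence. The main protection is continued follow-up. For exits that still occur, a sensitivity analysis should show the primary percentage with unknown outcomes counted both ways.

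**Cost.** Wording in both documents; no added visits or tests. The small downside is that a few ineligible subjects remain in the tables.
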